APPENDIX A PERFORMANCE STATUS CRITERIA

ECOG Performance Status Scale	
Grade	Descriptions
0	Normal activity. Fully active, able to carry on all pre-disease performance without restriction.
1	Symptoms, but ambulatory. Restricted in physically strenuous activity, but ambulatory and able to carry out work of a light or sedentary nature (e.g., light housework, office work).
2	In bed <50% of the time. Ambulatory and capable of all self-care, but unable to carry out any work activities. Up and about more than 50% of waking hours.
3	In bed >50% of the time. Capable of only limited self-care, confined to bed or chair more than 50% of waking hours.
4	100% bedridden. Completely disabled. Cannot carry on any self-care. Totally confined to bed or chair.
5	Dead.

APPENDIX B1 ACUTE GRAFT VERSUS HOST DISEASE WORKSHEET**Acute GVHD Worksheet**

Consensus Conference on Acute GVHD Grading

Reference: Przepiorka, DD et al., *Bone Marrow Transplant*, 825-828.**Instructions:**

1. Is acute GVHD present (circle): YES or NO
2. If yes, please circle below the Overall Grade (and the Individual Stages as Relevant)

GVHD Classification

Overall Grade (please circle)	Skin	Liver	Gut
I	Stage 1-2	None	None
II	Stage 3 or	Stage 1 or	Stage 1
III		Stage 2-3 or	Stage 2-4
IV	Stage 4 or	Stage 4	

For each overall grade of acute GVHD, an assessment of skin disease plus liver and/or gut is required.

Individual organ staging

Clinical manifestations and staging of acute GVHD

Organ	Clinical Manifestation	Staging	Tips to Investigator
Skin	Erythematous, maculopapular rash involving palms and soles; may become confluence; severe disease: bullae	Stage 1: < 25% rash Stage 2: 25-50% rash Stage 3: generalized erythroderma Stage 4: bullae	Use rule of 9s to determine extent of rash
Liver	Painless jaundice with conjugated hyperbilirubinemia and increased alkaline phosphatase	Stage 1: bilirubin 2-3 mg/dL Stage 2: bilirubin 3.1-6 mg/dL Stage 3: bilirubin 6.1-15 mg/dL Stage 4: bilirubin > 15 mg/dL	Range given is for total bilirubin; downgrade one stage if a cause of elevated bilirubin other than GvHD has been documented
GI	Upper: nausea, vomiting, anorexia Lower: diarrhea, abdominal cramps, distention, ileus, bleeding	Stage 1: diarrhea > 500 mL/day or persistent nausea or anorexia Stage 2: diarrhea > 1000 mL/day Stage 3: diarrhea > 1500 mL/day Stage 4: large volume diarrhea and severe abdominal pain +/- ileus	Downgrade one stage if a cause of diarrhea other than GvHD has been documented; downgrade upper GI one stage if biopsy result is negative; or if no biopsy is done and GvHD is not etiology or if biopsy is equivocal and GvHD is not an etiology

Subject ID:

Site:

Signature of Treating Investigator:

Date of evaluation:

Cycle/Day:

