5.2 Definition of Dose-Limiting Toxicity

DLT for dose-escalation purposes will be determined during the first 8 weeks of combination therapy (56 days from start of combination, starting cycle 1 day 1 of ipilimumab and decitabine) during the induction phase only. A DLT will be defined as any of the following toxicities that are determined to be *at least possibly* related to treatment with combination ipilimumab and decitabine and not related to underlying disease or intercurrent illness or to decitabine alone. Adverse events that occur after the first 8 weeks will also be evaluated by the investigator and may be considered dose limiting depending on the clinical scenario. Events will be graded by CTCAE v5.0 criteria.

DLTs include:

- Any study treatment related death (not due to disease or intercurrent illness).
- Acute GVHD that is an overall grade III or higher (see [Appendix B](#))
 - Exception: For skin GVHD alone, must be an overall grade II with at least stage 3 involvement or higher to be considered a DLT (skin GVHD that is stage 1-2 will not be considered a DLT).
- Grade 3 or higher non-hematologic toxicity
 - Exceptions:
 - Fatigue, nausea, weight loss, electrolyte abnormalities managed by replacement or correction, endocrine abnormalities managed by replacement therapy, skin rash, and those attributable to GVHD (as above)
 - Infections will be considered a DLT if grade 4 or higher or grade 3 that does not recover to grade 1 within 4 weeks
- Admission and IV antibiotics for neutropenic fever without sepsis or severe complication will not be considered a DLT (this is a frequent complication of underlying disease and of decitabine therapy)
- Grade 3 immune-related adverse events (e.g. diarrhea, pruritus, rash, endocrinopathies) that respond to corticosteroids and improve to grade 1 or less within 4 weeks will NOT count as DLTs. Optional biopsy of affected organs will be encouraged to help determine whether the immune-related condition is due to direct effects of ipilimumab versus GVHD.
- Grade 3 ipilimumab infusion reactions; a second consecutive occurrence or grade 4 or high infusion reaction will be considered a DLT.
- Grade 4 or higher hematologic toxicity will be considered a DLT if patients do not recover their absolute neutrophil count to $\geq 500 \times 10^9/L$ or platelet count to $\geq 25,000 \times 10^9/L$, at the end of the DLT window, with a hypocellular marrow and absence of

underlying disease.

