Suspicion for graft versus host disease (GVHD): If there is a concern for GVHD, then we recommend consideration of a biopsy for diagnostic work-up if clinically appropriate. Evidence of grade III or higher acute GVHD would be considered a DLT (except for skin GVHD, must have at least stage 3 involvement to be a DLT) as this often triggers systemic corticosteroids. These patients would stop receiving study treatment (both ipilimumab and decitabine), and followed for up to 1 year after treatment for AE resolution, response and survival. Those with skin GVHD that is overall grade II with stage 1-2 involvement or less will be able to stay on study. Topical corticosteroids are allowed. For GVHD events that are less than grade III, ipilimumab dose can be skipped (decitabine can continue) until event resolution or when the event is controlled without requiring systemic corticosteroids or immunosuppressive agents (exception: topical steroids) (missed ipilimumab doses will not be made up); these patients may remain on study. Please see [Appendix B](#) for resources to be used for acute and chronic GVHD grading.

It is necessary to delay ipilimumab dosing for the following related adverse events:

- Any \geq Grade 2 non-skin related adverse event (including immune related AE (irAEs)), except for asymptomatic laboratory abnormalities, grade 2-3 fatigue, and grade 2 anorexia (as the latter two events can be caused by disease alone). Treatment does not need to be delayed for controlled (on treatment) or recently treated infections.
- Any \geq Grade 3 non-hematologic laboratory abnormality except for grade 3 fatigue (as can be caused by disease). Treatment does not need to be delayed for controlled (on treatment) or recently treated infections.
- Any adverse event, laboratory abnormality or intercurrent illness that, in the judgment of the investigator, presents a substantial clinical risk to the subject with continued dosing
- Any \geq Grade 3 skin related adverse event (unless considered to be related to underlying disease, leukemia cutis, or a drug-allergy that is not due to study drug (ie antibiotics))
- An event that is not considered to be necessarily related to ipilimumab but requires a brief course of corticosteroid therapy.
 - An example, if a patient develops Sweet's syndrome (febrile neutrophilic dermatosis, confirmed by skin biopsy), then prednisone would be warranted. Patients would be allowed to continue decitabine to maintain disease control.

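### Read with Appendix B1, section 5.2 counts stage 3 skin GVHD alone as a DLT but not stage 3 skin plus stage 1 liver or gut, and section 6.2 does not settle the answer

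*Combined protocol and SAP*

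**What the plan says.** Three places bear on how acute GVHD is scored as a DLT.

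- **Section 5.2.** The general threshold is "Acute GVHD that is an overall grade III or higher". One exception follows: "For skin GVHD alone, must be an overall grade II with at least stage 3 involvement or higher to be considered a DLT". A parenthesis adds that skin GVHD at stage 1 or 2 does not count. The separate rule for grade 3 or higher non-hematologic toxicity lists among its exceptions "skin rash, and those attributable to GVHD (as above").
- **Section 6.2, paragraph on suspected GVHD.** The rule is restated as grade III or higher, "except for skin GVHD, must have at least stage 3 involvement to be a DLT". Patients with such a DLT stop both study drugs. The same paragraph says: "For GVHD events that are less than grade III, ipilimumab dose can be skipped (decitabine can continue"), and those patients may stay on study. It also lets patients with skin GVHD of overall grade II and stage 1-2 involvement stay on study.
- **Appendix B1.** The overall grade II row reads "Stage 3 or Stage 1 or Stage 1", for skin, liver and gut in that order. Grade III needs liver stage 2-3 or gut stage 2-4. Grade IV needs skin stage 4 or liver stage 4. The note under the grid says: "For each overall grade of acute GVHD, an assessment of skin disease plus liver and/or gut is required".

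**The concern.** A DLT rule should not score a patient as less toxic because a further organ is involved. In section 5.2 the lower bar applies only when skin is the sole organ. Stage 1 gut or liver disease takes the patient out of that exception without bringing the patient up to grade III.

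This affects a primary objective. Section 2.4 gives GVHD risk after transplant as the reason Arm A may need its own MTD or RP2D. Each escalation decision rests on three to six patients. The expansion-phase trigger in section 5.3 (two or more of six with a DLT) uses the same definition. Two investigators who both follow the protocol could score the same Arm A patient in opposite ways.

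**Working it through.** **1. Grade the pattern.** Under Appendix B1, stage 3 skin alone is overall grade II. Stage 3 skin with liver stage 1, gut stage 1, or both, meets no grade III or IV criterion, so it is also grade II.

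**2. Apply each section.** The 6.2 column uses the reading in which any skin stage of 3 or more is a DLT whatever the other organs show.

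| Skin | Liver | Gut | Overall grade | 5.2 | 6.2, any skin stage 3 or more |
|---|---|---|---|---|---|
| 3 | 0 | 0 | II | DLT | DLT |
| 3 | 0 | 1 | II | not DLT | DLT |
| 3 | 1 | 0 | II | not DLT | DLT |
| 3 | 1 | 1 | II | not DLT | DLT |
| 4 | any | any | IV | DLT | DLT |

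The non-hematologic route does not rescue rows 2 to 4, because skin rash and GVHD-attributable toxicity are both exempt there.

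**3. Extent.** With stages 0 to 4 in three organs there are 5 × 5 × 5 = 125 combinations. Coding both rules over all of them gives exactly three disagreements, rows 2 to 4. If *skin GVHD* in 6.2 means skin only, the two sections agree, and the drop from row 1 to rows 2-4 inside 5.2 remains.

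**4. The plan's own table.** Section 13.1 escalates on 0/3 or 1/6, so P(escalate) = (1−p)³ + 3p(1−p)²(1−p)³. For p = 0.10, 0.20, 0.30, 0.40 and 0.50 this gives 0.906, 0.709, 0.494, 0.309 and 0.172. The printed row (0.91, 0.71, 0.49, 0.31, 0.17) reproduces. The table is correct for whatever is counted as a DLT.

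**5. Illustration only.** Let q be the probability of the uncounted pattern. The documents do not give q, so the values here are assumed. Moving from not counting to counting the pattern changes the DLT rate from p to p + q:

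| Rate p counted under 5.2 | q = 0 | q = 0.05 | q = 0.10 |
|---|---|---|---|
| 0.10 | 0.906 | 0.814 | 0.709 |
| 0.20 | 0.709 | 0.600 | 0.494 |
| 0.30 | 0.494 | 0.396 | 0.309 |

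At q = 0 nothing changes, and nothing in the documents excludes a value close to that.

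**6. Single-patient effect.** This needs no rate. With no other DLT among three patients, one such patient makes the count 0/3 (escalate) or 1/3 (add at least three more). With one other DLT among six, the count is 1/6 (escalate) or 2/6 (stop).

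**7. Why deleting *alone* is unsafe.** The exception would then speak of skin GVHD generally, next to a parenthesis saying stage 1-2 does not count. Skin stage 1 or 2 with liver or gut at stage 2 or more is overall grade III or IV. That is 2 skin stages × (25 − 4) liver-gut pairs = 42 combinations that could be read as exempt, against the three being repaired.

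**The case against.** The best defense is that *skin GVHD* in 6.2 is shorthand for the skin-only exception in 5.2. If it meant any GVHD that includes skin, the 6.2 exception would also remove grade III gut disease with a stage 1 rash from the DLT count, which cannot be intended. This largely stands. A reader might infer that 5.2 and 6.2 flatly contradict each other, and the text does not establish that.

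The skin-only reading is not secure either. Section 6.2 speaks of skin GVHD of overall grade II with stage 1-2 involvement. Under Appendix B1, skin alone at stage 1-2 is grade I, so that phrase either includes a patient with stage 1 liver or gut disease or is a drafting slip. For the patient at issue, 6.2 supports two outcomes: a DLT with both drugs stopped, or GVHD below grade III with the patient staying on study.

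There are also safeguards. Suspected GVHD goes to the overall PI for central review (7.3.5). Escalation needs PI sign-off, with at least monthly calls that include CTEP (12.1). A 0/3 level may be expanded to six at the PI's discretion (5.1, 13.1). These make an unexamined escalation less likely, but none of them says whether the event is a DLT.

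Finally, the pattern is narrow. The earlier post-transplant study described in section 2.4 lists one grade II acute gut GVHD among the dose-limiting effects at 10 mg/kg, and describes no case of stage 3 skin with liver or gut disease. This stands: the documents give no evidence on how often the pattern occurs.

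**Conclusion.** The gap in 5.2 is real and follows from the plain words of 5.2 and the Appendix B1 grid. Three grade II combinations are not DLTs although the same skin disease without the second organ is one. Section 6.2 does not resolve this, because it can be read to give either answer. The Appendix B1 grid itself is not at fault.

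A reader might infer that the rule inflates escalation in Arm A by a known amount. The documents do not support that. They give no frequency, so the shift in P(escalate) is unknown and may be near zero, and the figures in the illustration depend wholly on assumed rates. What can be said is that one such patient would decide an Arm A dose step, and that not counting these events can only lower the DLT count compared with counting them. Whether they ought to count is a clinical decision for the sponsor.

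**What to change.** Reconcile section 5.2, section 6.2 and Appendix B1 into one DLT-scoring clause, worded identically wherever it appears, that meets two conditions:

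1. Adding liver or gut involvement never turns a DLT into a non-DLT.
2. No overall grade III or IV event is exempted because its skin stage is low.

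Print the resulting skin × liver × gut DLT grid on the Appendix B1 worksheet, so that every combination has one answer. Do not simply delete *alone*.

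The sponsor must choose the threshold. Because 6.2 ties a GVHD DLT to stopping both drugs, the sponsor must also state the treatment consequence that goes with it. The cost is one amended clause and one table. Depending on how the passages are reconciled, a few more or a few fewer grade II events may count as DLTs in Arm A.

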APPENDIX B2 CHRONIC GRAFT VERSUS HOST DISEASE WORKSHEET

Chronic GVHD Worksheet

Consensus Conference on Acute GVHD Grading

Reference: Jagasia MH et al., Biol Blood Marrow Transplant, 2015, 389-401.

Instructions:

1. Is chronic GVHD present (circle): YES or NO
2. If yes, please circle global severity below (mild, moderate or severe). See sheets on Scoring per organ

Mild	
 • 1 or 2 organs or sites (except lung) with score 1 
 • Mild oral symptoms, no decrease in oral intake • Mild dry eyes, lubricant eyedrops \leq 3x/day
Moderate	
 • 3 or more organs with score 1 • At least 1 organ or site with score 2 
 • 19-50% body surface area involved or superficial sclerosis • Moderate dry eyes, eyedrops $>$ 3x/day or punctal plugs • Lung score 1 (FEV1 60-79% or dyspnea with stairs)
Severe	
 • At least 1 organ or site with score 3 
 • $>$ 50% body surface area involved • Deep sclerosis, impaired mobility or ulceration • Severe oral symptoms with major limitation in oral intake • Severe dry eyes affecting ADL • Lung score 2 (FEV1 40-59% or dyspnea walking on flat ground)

Figure 4. Calculation of mild, moderate, and severe global severity, with examples. If the entire abnormality in an organ is noted to be unequivocally explained by a non-GVHD documented cause, that organ is not included for calculation of the global severity. If the abnormality in an organ is attributed to multifactorial causes (GVHD plus other causes) the scored organ will be used for calculation of the global severity regardless of the contributing causes (no downgrading of organ severity score). ADL, activities of daily living; FEV1, forced expiratory volume in 1 second.

Subject ID:

Site:

Signature of Treating Investigator:

Date of evaluation:

Cycle/Day:

	SCORE 0	SCORE 1	SCORE 2	SCORE 3
PERFORMANCE SCORE:  KPS ECOG LPS	 Asymptomatic and fully active (ECOG 0; KPS or LPS 100%)	 Symptomatic, fully ambulatory, restricted only in physically strenuous activity (ECOG 1, KPS or LPS 80-90%)	 Symptomatic, ambulatory, capable of self-care, >50% of waking hours out of bed (ECOG 2, KPS or LPS 60-70%)	 Symptomatic, limited self-care, >50% of waking hours in bed (ECOG 3-4, KPS or LPS <60%)

SKIN†**SCORE % BSA****GVHD features to be scored by BSA:****Check all that apply:**

- Maculopapular rash/erythema
- Lichen planus-like features
- Sclerotic features
- Papulosquamous lesions \diamond chthyosis
- Keratosis pilaris-like GVHD

 No BSA involved 1-18% BSA 19-50% BSA >50% BSA**SKIN FEATURES****SCORE:** No sclerotic features Superficial sclerotic features "not hidebound" (able to pinch)**Check all that apply:**

- Deep sclerotic features
- "Hidebound" (unable to pinch)
- Impaired mobility
- Ulceration

Other skin GVHD features (NOT scored by BSA)**Check all that apply:**

- Hyperpigmentation
- Hypopigmentation
- Poikiloderma
- Severe or generalized pruritus
- Hair involvement
- Nail involvement

Y Abnormality present but explained entirely by non-GVHD documented cause (specify):

MOUTH Lichen planus-like features present:	 No symptoms	 Mild symptoms with disease signs but not limiting oral intake	 Moderate symptoms with disease signs with partial limitation of oral intake	 Severe symptoms with disease signs on examination with major limitation of oral intake
 Yes				
 No				

Y Abnormality present but explained entirely by non-GVHD documented cause (specify):

	SCORE 0	SCORE 1	SCORE 2	SCORE 3
EYES Keratoconjunctivitis sicca (KCS) confirmed by ophthalmologist:  Yes  No  Not examined	 No symptoms	 Mild dry eye symptoms not affecting ADL (requirement of lubricant eye drops ≤ 3 x per day)	 Moderate dry eye symptoms partially affecting ADL (requiring lubricant eye drops > 3 x per day or punctal plugs), WITHOUT new vision impairment due to KCS	 Severe dry eye symptoms significantly affecting ADL (special eyeware to relieve pain) OR unable to work because of ocular symptoms OR loss of vision due to KCS

Abnormality present but explained entirely by non-GVHD documented cause (specify):

GI Tract Check all that apply:  Esophageal web/ proximal stricture or ring  Dysphagia  Anorexia  Nausea  Vomiting  Diarrhea  Weight loss $\geq 5\%$ *  Failure to thrive	 No symptoms	 Symptoms without significant weight loss* ($<5\%$)	 Symptoms associated with mild to moderate weight loss* (5-15%) OR moderate diarrhea without significant interference with daily living	 Symptoms associated with significant weight loss* $>15\%$, requires nutritional supplement for most calorie needs OR esophageal dilation OR severe diarrhea with significant interference with daily living
---	---	--	---	--

Abnormality present but explained entirely by non-GVHD documented cause (specify):

LIVER	 Normal total bilirubin and ALT or AP $< 3 \times$ ULN	 Normal total bilirubin with ALT ≥ 3 to 5 \times ULN or AP $\geq 3 \times$ ULN	 Elevated total bilirubin but ≤ 3 mg/dL or ALT > 5 ULN	 Elevated total bilirubin > 3 mg/dL
 Abnormality present but explained entirely by non-GVHD documented cause (specify):				
LUNGS** Symptom score:	 No symptoms	 Mild symptoms (shortness of breath after climbing one flight of steps)	 Moderate symptoms (shortness of breath after walking on flat ground)	 Severe symptoms (shortness of breath at rest; requiring O ₂)
Lung score:  FEV1 $\geq 80\%$  % FEV1	 FEV1 $\geq 80\%$	 FEV1 60-79%	 FEV1 40-59%	 FEV1 $\leq 39\%$

Pulmonary function tests

Not performed

Abnormality present but explained entirely by non-GVHD documented cause (specify):

JOINTS AND FASCIA	 No symptoms	 Mild tightness of arms or legs, normal or mild decreased range of motion (ROM) AND not affecting ADL	 Tightness of arms or legs OR joint contractures, erythema thought due to fasciitis, moderate decrease ROM AND mild to moderate limitation of ADL	 Contractures WITH significant decrease of ROM AND significant limitation of ADL (unable to tie shoes, button shirts, dress self etc.)
P-ROM score (see below)				
Shoulder (1-7): _____				
Elbow (1-7): _____				
Wrist/finger (1-7): _____				
Ankle (1-4): _____				

Abnormality present but explained entirely by non-GVHD documented cause (specify):

GENITAL TRACT (See Supplemental figure[†])	 No signs	 Mild signs [‡] and females with or without discomfort on exam	 Moderate signs [‡] and may have symptoms with discomfort on exam	 Severe signs [‡] with or without symptoms
 Not examined				
Currently sexually active				
 Yes				
 No				

[figure not shown]
Abnormality present but explained entirely by non-GVHD documented cause (specify):

Other indicators, clinical features or complications related to chronic GVHD (check all that apply and assign a score to severity (0-3) based on functional impact where applicable none – 0, mild -1, moderate -2, severe – 3)

 Ascites (serositis)	 Myasthenia Gravis_____
 Pericardial Effusion	 Peripheral Neuropathy_____
 Pleural Effusion(s)	 Polymyositis_____
 Nephrotic syndrome	 Weight loss>5%* without GI symptoms  Others (specify): _____

Overall GVHD Severity
(Opinion of the evaluator)

No GVHD Mild Moderate Severe

Photographic Range of Motion (P-ROM)

† Skin scoring should use both percentage of BSA involved by disease signs and the cutaneous features scales. When a discrepancy exists between the percentage of total body surface (BSA) score and the skin feature score, OR if superficial sclerotic features are present (Score 2), but there is impaired mobility or ulceration (Score 3), the higher level should be used for the final skin scoring.

* Weight loss within 3 months.

**Lung scoring should be performed using both the symptoms and FEV1 scores whenever possible. FEV1 should be used in the final lung scoring where there is discrepancy between symptoms and FEV1 scores.

Abbreviations: ECOG (Eastern Cooperative Oncology Group), KPS (Karnofsky Performance Status), LPS (Lansky Performance Status); BSA (body surface area); ADL (activities of daily living); LFTs (liver function tests); AP (alkaline phosphatase); ALT (alanine aminotransferase); ULN (normal upper limit).

[figure not shown]
‡ To be completed by specialist or trained medical providers (see Supplemental Figure).

APPENDIX C

MANAGEMENT OF IMMUNE-RELATED ADVERSE EVENTS,
DIARRHEA, HEPATOTOXICITY, ENDOCRINOPATHY, SKIN
AND NEUROPATHY *

*Investigator's Brochure (March 2016)

[figure not shown]
General Recommendations for Management of Suspected Inflammatory Events

* Based on clinical experience to date, systemic steroids for treatment of irAEs do not appear to impact the development or maintenance of ipilimumab clinical activity in advanced melanoma.

Diarrhea Management Algorithm

GI Toxicity Management Algorithm

Patients on IV steroids may be switched to oral corticosteroid (e.g., prednisone) at an equivalent dose at start of tapering or earlier, once sustained clinical improvement is observed. Lower bioavailability of oral corticosteroids should be taken into account when switching to the equivalent dose of PO corticosteroids.

Diarrhea				
GRADE 1	GRADE 2	GRADE 3	GRADE 4	GRADE 5
Increase of <4 stools per day over baseline; mild increase in ostomy output compared with baseline	Increase of 4-6 stools per day over baseline; IV fluids indicated < 24 hrs; moderate increase in ostomy output compared to baseline; not interfering with activities of daily living (ADL)	Increase of ≥7 stools per day over baseline; incontinence; IV fluids ≥ 24 hrs; hospitalization; severe increase in ostomy output compared to baseline; interfering with ADL	Life-threatening consequences (e.g., hemodynamic collapse)	Death

[figure not shown]
Hepatotoxicity Management Algorithm

Situation: rising liver function tests (LFTs) >8X ULN or suspected immune-mediated hepatitis

- 1) Admit subject to hospital for evaluation and close monitoring
- 2) Stop further ipilimumab dosing until hepatotoxicity is resolved. Consider permanent discontinuation of ipilimumab per protocol
- 3) Start at least 120 mg methylprednisolone sodium succinate per day, given IV as a single or divided dose
- 4) Check liver laboratory test values (LFTs, T-bilirubin) daily until stable or showing signs of improvement for at least 3 consecutive days
- 5) If no decrease in LFTs after 3 days or rebound hepatitis occurs despite treatment with corticosteroids, then add mycophenolate mofetil 1g BID per institutional guidelines for immunosuppression of liver transplants (supportive treatment as required, including prophylaxis for opportunistic infections per institutional guidelines)
- 6) If no improvement after 5 to 7 days, consider adding 0.10 to 0.15 mg/kg/day of tacrolimus (trough level 5-20 ng/mL)
- 7) If target trough level is achieved with tacrolimus but no improvement is observed after 5 to 7 days, consider infliximab, 5 mg/kg, once
- 8) Continue to check LFTs daily for at least 2 weeks to monitor sustained response to treatment

A flow chart of the algorithm is depicted on the following page.

Hepatotoxicity Management Algorithm

[figure not shown]
*Ipilimumab may be held/delayed rather than discontinued if AST/ALT $\leq 8 \times$ ULN and Tbili $\leq 5 \times$ ULN. Resume ipilimumab when AST/ALT/Tbili return to grade 2 and meet protocol specific retreatment criteria.

**The recommended starting dose for grade 4 hepatitis is 2 mg/kg/day methylprednisolone IV.

*** MMF, mycophenolate mofetil

Patients on IV steroids may be switched to oral corticosteroid (e.g., prednisone) at an equivalent dose at start of tapering or earlier, once sustained clinical improvement is observed. Lower bioavailability of oral corticosteroids should be taken into account when switching to the equivalent dose of PO corticosteroids.

Endocrinopathy Management Algorithm

[figure not shown]

↑

Patients on IV steroids may be switched to oral corticosteroid (e.g., prednisone) at an equivalent dose at start of tapering or earlier, once sustained clinical improvement is observed. Lower bioavailability of oral corticosteroids should be taken into account when switching to the equivalent dose of PO corticosteroids.

[figure not shown]
*Patients with adrenal insufficiency might need to continue steroids with mineralocorticoid component as substitution

Skin Toxicity Management Algorithm

Patients on IV steroids may be switched to oral corticosteroid (e.g., prednisone) at an equivalent dose at start of tapering or earlier, once sustained clinical improvement is observed. Lower bioavailability of oral corticosteroids should be taken into account when switching to the equivalent dose of PO corticosteroids.

Neurological Toxicity Management Algorithm

Patients on IV steroids may be switched to oral corticosteroid (e.g., prednisone) at an equivalent dose at start of tapering or earlier, once sustained clinical improvement is observed. Lower bioavailability of oral corticosteroids should be taken into account when switching to the equivalent dose of PO corticosteroids.

